# 7.2.2.1. Monotherapy Arm A

In case of toxicity, IFX-1 dosing can be held by a maximum of 4 weeks. If therapy is continued during this time span, dosing will resume within the initial schedule and allowed administration window for a specific visit.

IFX-1 has the potential to elicit infusion-related reactions, including hypersensitivity or anaphylaxis. Treatment modification criteria due to infusion-related reactions are listed in Appendix 8, Table 5.

For treatment discontinuation criteria, see Section 7.2.4.

There are no DLTs defined for Arm A.

# 7.2.2.2. Combination Therapy Arm B

In case of toxicity, IFX-1 dosing can be held by a maximum of 4 weeks and pembrolizumab dosing by a maximum of 12 weeks. If therapy is continued during this time span, dosing will resume within the initial schedule and allowed administration window for a specific visit.

For treatment modifications due to irAEs, see Section 7.2.2.2.1 and due to infusion-related reactions, see Section 7.2.2.2.2.

IFX-1 and pembrolizumab may be interrupted for situations other than treatment-related AEs such as medical/surgical events or logistical reasons not related to study therapy. However, pembrolizumab is to be restarted within 6 weeks or 42 days of the originally scheduled dose and within 12 weeks or 84 days of the previously administered dose, unless otherwise discussed with the Sponsor. IFX-1 is to be restarted within 2 weeks or 14 days of the originally scheduled dose and within 4 weeks or 28 days of the previously administered dose. The interruption shall not lead to a longer dosing interval than 4 weeks for IFX-1 and 12 weeks for pembrolizumab. The reason for interruption should be documented in the patient's study record.

For treatment discontinuation criteria, see Section 7.2.4.

# **7.2.2.2.1.** Immune-Related Adverse Events

AEs associated with pembrolizumab exposure may represent an immune-related response. These irAEs may occur shortly after the first dose or several months after the last dose of pembrolizumab treatment and may affect more than one body system simultaneously. Therefore, early recognition and initiation of treatment is critical to reduce complications. Based on existing clinical study data, most irAEs were reversible and could be managed with interruptions of pembrolizumab, administration of corticosteroids, and/or other supportive care. For suspected irAEs, ensure adequate evaluation to confirm etiology or exclude other causes. Additional procedures or tests such as bronchoscopy, endoscopy, and skin biopsy may be included as part of the evaluation. Dose modification criteria for pembrolizumab in response to Grade 2 or higher irAEs are listed in

Appendix 8, Table 4. If treatment should be withheld due to toxicity, both pembrolizumab and IFX-1 should be withheld (see Appendix 8, Table 4).

#### 7.2.2.2.2. Infusion-Related Reactions

IFX-1 as well as pembrolizumab may cause severe or life-threatening infusion-related reactions, including severe hypersensitivity or anaphylaxis. Signs and symptoms usually develop during or shortly after drug infusion and generally resolve completely within 24 hours of completion of infusion. Dose modification criteria for infusion-related reactions are listed in Appendix 8, Table 5.

# **7.2.2.2.3.** Dose-Limiting Toxicities

DLTs are only defined for combination Arm B. All DLTs will be graded using NCI-CTCAE Version 5.0 based on the investigator assessment.

A DLT is a toxicity that occurs during the DLT assessment period up to and including Cycle 1 treatment day 36 and is assessed by the investigator as being possibly, probably, or definitely related to study treatment administration. DLTs are defined by the following:

- 1. Nonhematologic toxicity (not laboratory):
  - Drug related Grade 3 or 4 infections and infestations
  - Any treatment-related toxicity that causes the patient to discontinue treatment; see Appendix 8, Table 4 for dose modification criteria in case of irAEs, and Table 5 in case of infusion-related reactions
- 2. Grade 4 hematologic toxicity lasting  $\geq 7$  days, except thrombocytopenia:
  - Grade 4 thrombocytopenia of any duration
  - Grade 3 thrombocytopenia associated with clinically significant bleeding that may require transfusion, invasive intervention, or hospitalization
- 3. Any nonhematologic AE ≥Grade 3 in severity should be considered a DLT, with the following exceptions: Grade 3 fatigue lasting ≤ 3 days; Grade 3 diarrhea, nausea, or vomiting without use of anti-emetics or anti-diarrheals per standard of care; Grade 3 rash without use of corticosteroids or anti-inflammatory agents per standard of care.
- 4. Any Grade 3 or Grade 4 non-hematologic laboratory value if:
  - Clinically significant medical intervention is required to treat the participant or
  - The abnormality leads to hospitalization, or

- The abnormality persists for >1 week.
- The abnormality results in a Drug-induced Liver Injury (DILI)
- 5. Febrile neutropenia Grade 3 or Grade 4:
  - Grade 3 is defined as ANC <1000/mm³ with a single temperature of >38.3 degrees C (101 degrees F) or a sustained temperature of ≥38 degrees C (100.4 degrees F) for more than 1 hour
  - Grade 4 is defined as ANC <1000/mm³ with a single temperature of >38.3 degrees C (101 degrees F) or a sustained temperature of ≥38 degrees C (100.4 degrees F) for more than 1 hour, with life-threatening consequences and urgent intervention indicated.
- 6. Prolonged delay (>2 weeks) in initiating Cycle 2 due to treatment-related toxicity.
- 7. Any treatment-related toxicity that causes the participant to discontinue treatment during Cycle 1.
- 8. Missing >25% of 1 or both IND doses (IFX-1 and/or pembrolizumab) doses as a result of drug-related AE(s) during the first cycle.
- 9. Grade 5 toxicity.

The frequency, time to onset, and severity of toxicities, as well as the success of standard medical management and dosing interruptions/delays, will be analyzed to determine if a given toxicity should be considered a DLT for dose escalation purposes.

TEAEs that appear to meet the DLT definition will be discussed between the investigator, the sponsor and the steering committee (see Section 5.3.2). The final decision of whether or not the AE meets the DLT definition will be based on a careful review of all relevant data and consensus between the investigator, sponsor, and steering committee.

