#### General instructions:

- 1. Severe and life-threatening irAEs should be treated with intravenous corticosteroids followed by oral steroids. Other immunosuppressive treatment should begin if the irAEs are not controlled by corticosteroids.
- 2. Pembrolizumab must be permanently discontinued if the irAE does not resolve or the corticosteroid dose is not ≤10 mg/day within 12 weeks of the last pembrolizumab treatment.
- 3. The corticosteroid taper should begin when the irAE is  $\leq$ Grade 1 and continue  $\geq$ 4 weeks.

4. If pembrolizumab and IFX-1 have been withheld, pembrolizumab and/or IFX-1 may resume after the irAE decreased to ≤Grade 1 after corticosteroid taper.

	Toxicity Grade	Action with	Corticosteroid and/or		
	(CTCAE v5.0)	pembrolizumab	other therapies		
irAEs		and IFX-1		Monitoring and follow-up	
	Grade 2	Withhold	Administer corticosteroids (initial dose of 1 to 2 mg/kg prednisone or equivalent)	
 
Monitor patients for signs and symptoms of pneumonitis
 
Evaluate patients with
 
	
Pneumonitis	Recurrent Grade 2, Grade 3 or 4	Permanently discontinue	followed by taper  • Add prophylactic antibiotics for opportunistic infections	suspected pneumonitis with radiographic imaging and initiate corticosteroid treatment	
	Grade 2 or 3	Withhold	Administer corticosteroids (initial dose of 1 to 2 mg/kg prednisone or equivalent) followed by taper	• Monitor patients for signs and symptoms of enterocolitis (i.e., diarrhea, abdominal pain, blood or mucus in stool with or without fever) and of bowel perforation (i.e., peritoneal	
Diarrhea/Colitis	Recurrent Grade 3 or Grade 4	Permanently discontinue		signs and ileus)  • Patients with ≥Grade 2 diarrhea suspecting colitis should consider GI consultation and performing endoscopy to rule out colitis  • Patients with diarrhea/colitis should be advised to drink liberal quantities of clear fluids. If sufficient oral fluid intake is not feasible, fluid and electrolytes should be substituted via intravenous infusion	
AST or ALT elevation or increased bilirubin	Grade 2 ª	Withhold	Administer corticosteroids (initial dose of 0.5 to 1 mg/kg prednisone or equivalent) followed by taper	Monitor with liver function tests (consider weekly or more frequently until liver enzyme value returned to baseline or is stable)	

	Grade 3 b or 4 c	Permanently	Administer		
State 3 of 1		discontinue	corticosteroids (initial dose of 1 to 2 mg/kg		
			prednisone or equivalent) followed by taper		

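### DLT item 3 lets a steroid-treated first Grade 3 immune-related diarrhea stay exempt, and after the Day 22 infusion no other numbered item can count it at the Day 36 review

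*Combined protocol and SAP*

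**What the plan says.** Item 3 of section 7.2.2.2.3 makes any nonhematologic AE of Grade 3 or higher a DLT, with exceptions. Two of them read: "Grade 3 diarrhea, nausea, or vomiting without use of anti-emetics or anti-diarrheals per standard of care; Grade 3 rash without use of corticosteroids", the rash clause going on to name anti-inflammatory agents.

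Appendix 8, Table 4 covers Grade 2 or 3 diarrhea/colitis. The action is to withhold. The treatment is "Administer corticosteroids (initial dose of 1 to 2 mg/kg prednisone or equivalent) followed by taper", with fluids, and no anti-diarrheal is listed. Only recurrent Grade 3 or Grade 4 leads to permanent discontinuation. Patients with diarrhea of Grade 2 or higher and suspected colitis "should consider GI consultation and performing endoscopy to rule out colitis". General instruction 3 starts "The corticosteroid taper should begin when the irAE is" and sets the start at Grade 1 or lower and the length at 4 weeks or more. Dosing may resume after the taper.

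Section 7.2.2.2.1 adds: "If treatment should be withheld due to toxicity, both pembrolizumab and IFX-1 should be withheld".

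Two other items bear on a withheld patient:
- Item 8: "Missing >25% of 1 or both IND doses" in the first cycle because of drug-related AEs.
- Item 6: "Prolonged delay (>2 weeks) in initiating Cycle 2 due to treatment-related toxicity".

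The DLT window runs through Cycle 1 Day 36. Section 5.3.2 has the steering committee review each cohort once 3 patients have reached that day. Section 7.2.2.2.2 of the dose-modification rules aside, section 7.2.2.2 caps an IFX-1 hold for toxicity at 4 weeks and has dosing resume at a scheduled visit.

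**The concern.** The exception should separate a self-limiting Grade 3 event from one that needed treatment. For rash it does so with the treatment used for an immune-related rash. For diarrhea it names symptomatic medicines only, while the protocol's own treatment for the immune-related form is corticosteroids. A site that follows Table 4 exactly can therefore produce an exempt event.

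The label also decides the outcome. Colitis is not in the exception, so the same illness recorded as Grade 3 colitis is a DLT. Table 4 only asks sites to consider the endoscopy that would tell the two apart.

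DLT frequency by cohort is the primary endpoint of the Arm B run-in (section 4.2.1.2) and sets the MTD or RP2D. Section 3.2.3.2 lists immune-related events, colitis among them, as major on-target effects of pembrolizumab. The misclassification runs in the unsafe direction: a steroid-treated Grade 3 toxicity is left out of the count.

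**Working it through.** **1. Inputs.** IFX-1 in Cycle 1 is given on Days 1, 4, 8, 15, 22 and 36, which is 6 doses; pembrolizumab is given once, on Day 8 (sections 7.2 and 7.2.1.2). Cycle 1 lasts 49 days (section 7.2.1.1), so Cycle 2 Day 1 is Day 50. The taper is at least 28 days. The documents do not give the time from onset to Grade 1, so I call it r and take 1 to 14 days as an assumption. Onset day is t.

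**2. Item 3.** Grade 3, corticosteroids, no anti-emetic or anti-diarrheal: exempt. Reading the exception as covering events for which standard anti-diarrheals have not yet been tried gives the same answer.

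**3. Item 8 (more than 25% missed).**
- Onset before the Day 22 infusion: at least Days 22 and 36 are missed, 2/6 = 33.3% by count and 50% by mg. Item 8 is met.
- Onset after the Day 22 infusion and before the Day 36 infusion: only Day 36 is missed, 1/6 = 16.7% by count. By mg the share is 800/(4×400 + 2×800) = 800/3200, 1200/(4×600 + 2×1200) = 1200/4800 and 1600/(4×800 + 2×1600) = 1600/6400 for regimens 1 to 3. Each is exactly 25.0%. Item 8 is not met.
- Onset after the Day 36 infusion: 0/6. Item 8 is not met.
- No Cycle 1 pembrolizumab dose is missed in any of these cases, because the only one falls on Day 8.

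**4. Items 1 and 7 (discontinuation).** A first Grade 3 episode is withheld, not discontinued. A 28-day hold that begins on Day 22 ends on Day 50, after Cycle 1 has closed, so reaching the cap does not trigger item 7.

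**5. Item 6 and the 4-week cap.** The earliest restart is t + r + 28. Item 6 needs a restart after Day 50 + 14 = Day 64. The cap, counted from the missed Day 36 dose, is passed after Day 36 + 28 = Day 64. Both therefore require t + r > 36, and neither is established at the Day 36 review.

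For onset Days 22 (after dosing) to 36, a taper of exactly 28 days gives:

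| r (days, assumed) | Item 6 met, but only later | May meet no numbered item (t + r of 36 or less) |
|---|---|---|
| 1 | Day 36 (1 day) | Days 22–35 (14 days) |
| 3 | Days 34–36 (3) | Days 22–33 (12) |
| 7 | Days 30–36 (7) | Days 22–29 (8) |
| 14 | Days 23–36 (14) | Day 22 (1) |

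Restarts must fall on scheduled visits. With t = 22 and r = 7 the earliest restart is Day 57, and the next visit is Day 64 (±3 days). A restart on Days 61 to 64 is a delay of 11 to 14 days, so item 6 is not met; a restart on Days 65 to 67 would meet it.

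**6. Remaining items.** Items 2, 4, 5 and 9 do not cover diarrhea as such.

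**7. Effect under the 3+3 rule (section 10.3.4.2), cohort of 3, no other DLT.**

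| Such events | Count by the written list | Count if corticosteroids are named |
|---|---|---|
| 1 | 0/3: escalate | 1/3: add 3 patients |
| 2 | 0/3: escalate | 2/3: stop the regimen |

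**The case against.** The strongest answer is discretion. Near its end, section 7.2.2.2.3 says that onset, severity, the success of medical management and dosing interruptions will be analyzed to decide whether a toxicity counts as a DLT for escalation. That reaches any toxicity and describes this one well. Section 5.3.2 also gives the committee all safety data before each meeting. This stands: a reader might infer that the next regimen opens automatically on 0/3, and the documents do not support that. It does not remove the defect. The consensus step that follows is written for a narrower set: "TEAEs that appear to meet the DLT definition will be discussed between the investigator, the sponsor and the steering committee". An expressly exempted event does not obviously qualify. Section 5.3 has the committee review AE data in line with the same DLT definition.

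A second answer is the 4-week IFX-1 cap. Counted from onset, every such hold exceeds 28 days, because r is at least 1. Counted from the Day 22 dose, the earliest restart is Day 51, which is 29 days. Either count implies stopping IFX-1 and so item 1, which is not limited to Cycle 1. A prescribed 4-week taper also makes the overrun foreseeable at Day 36. But the protocol does not say where the count starts for a toxicity hold, and its dosing-interval sentence sits in the paragraph on interruptions for other reasons. On each reading the cap is passed only after Day 36.

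Third, the scenario is narrow: a first Grade 3 event, steroids, no anti-diarrheal, recorded as diarrhea, onset after the Day 22 infusion. Appendix 6 II prefers the diagnosis to the symptom, and section 7.2.2.2.1 asks for adequate evaluation of etiology, so some cases will be recorded as colitis and counted. Patients who stopped earlier checkpoint therapy for a severe irAE are excluded. All of this limits frequency; none of it changes the classification.

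**Conclusion.** The point holds as a gap in the written list. A first Grade 3 immune-related diarrhea managed as Table 4 directs and recorded as diarrhea is exempt under item 3. With onset after the Day 22 infusion, no other numbered item can count it at the Day 36 review. If t + r exceeds 36, item 6 (or item 1 through the hold cap) can count it later; otherwise it may never meet a numbered item.

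Onset Days 22 to 36 are 15 of the 29 days from Day 8 to Day 36. A reader might take that as the share of events never caught. It is only the share of onset days not settled at Day 36; with r = 7, for example, 7 of those 15 are caught later. Nor is it a risk estimate: the documents give no event rate, so the probability of a wrong escalation cannot be calculated.

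The result assumes the literal text, a 28-day taper, r of 1 to 14 days and the hold cap counted from the first missed dose. It should be fixed because the run-in's primary endpoint ought not to depend on a committee overriding a written exemption.

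**What to change.** In section 7.2.2.2.3, item 3, add corticosteroids to the medicines whose use removes the exemption for Grade 3 diarrhea, nausea or vomiting, and add: *This exception does not apply to diarrhea managed as an irAE under Appendix 8, Table 4.* The change only tightens the definition and brings it into line with the rash exception in the same sentence. It also removes most of the dependence on whether the event is recorded as diarrhea or colitis.

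No new data are needed: grade, start and stop times and corrective treatment are already recorded for each AE (section 9). The cost is that a cohort of 3 with one such event and no other DLT expands by 3 patients under the existing rule. Two such events would stop the regimen, which is what the 3+3 rule intends for two counted toxicities.

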# 5.3.2. Combination Therapy Arm B

In Arm B, during the safety run-in for each combination regimen cohort, the first 2 patients must be enrolled sequentially separated by a minimum of one week.

At the following time points, the Committee will review patient safety:

- For the very first patient receiving the combination therapy: After Cycle 1, Day 36, when this patient will have received the four consecutive IFX-1 fractionated loading dose administrations, one pembrolizumab administration, and two of the higher IFX-1 Q2W doses (to allow inclusion of subsequent patients)
- For each escalating dosing regimen: After 3 patients of each combination regimen cohort will have reached Cycle 1, day 36, at which they will have received the four consecutive IFX-1 fractionated loading dose administrations, one pembrolizumab administration, and two of the higher IFX-1 Q2W doses (to determine occurrence of DLT and necessity to include 3 more patients in a given dose cohort, to allow treatment in the next higher dose cohort, or to determine the MTD or RP2D)

To determine the RP2D, 6 patients should be treated at the MTD or highest dose level. If only 3 patients will have been enrolled into the respective cohort, 3 more patients will be enrolled at the same dose level. If no further toxicities are observed, this MTD will be selected as dose for Stage 2 and recommended combination regimen. Further patient enrollment in Arm B can proceed without specific rules.

The steering committee will continue to meet every three months until the last patient will have completed the third month of treatment in Stage 1 of the study and every six months thereafter to further confirm safety of the MTD or RP2D, and to further assess general safety of study treatment administration. All available safety data will be provided to the steering committee before each meeting.

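### Arm B dose escalation is decided when three patients reach Day 36, before some DLT criteria can be settled, with no required hold and no rule for a DLT confirmed later

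*Combined protocol and SAP*

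**What the plan says.** Section 7.2.2.2.3 counts related toxicities arising in the "DLT assessment period up to and including Cycle 1 treatment day 36". Several criteria then depend on what happens afterwards:

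- Criterion 6: "Prolonged delay (>2 weeks) in initiating Cycle 2 due to treatment-related toxicity".
- Criterion 4, duration limb for Grade 3 or 4 non-hematologic laboratory values: "The abnormality persists for >1 week". Criterion 2 similarly needs a Grade 4 hematologic toxicity to last at least 7 days.
- Criterion 8: more than 25% of one or both drugs' "doses as a result of drug-related AE(s) during the first cycle".

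Section 5.3.2 sets the cohort review after three patients have reached Day 36, "to determine occurrence of DLT and necessity to include 3 more patients in a given dose cohort", and to allow the next dose cohort. Within a cohort, "the first 2 patients must be enrolled sequentially separated by a minimum of one week". The very first combination patient is reviewed alone at Day 36 before others enter. Section 10.3.4.2 escalates on 0 of 3 or 1 of 6.

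Section 7.2.2.2.3 also says that dosing interruptions and delays will be analyzed when deciding whether a toxicity is a DLT for escalation, and that "TEAEs that appear to meet the DLT definition will be discussed between the investigator, the sponsor and the steering committee".

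**The concern.** The review that decides escalation is tied to Day 36, but a toxicity that arises by Day 36 can become a DLT weeks later. A cohort can then be cleared as 0 of 3 when the completed count is 1 of 3 (expand rather than escalate). In an expanded cohort, 1 of 6 can stand in for 2 of 6 (stop). The error runs only towards escalation.

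DLT frequency by cohort is the primary endpoint of the run-in (section 4.2.1.2) and leads to the MTD or RP2D used in Stage 2. The protocol does not say whether a DLT confirmed after the review changes its cohort's count, or what happens to patients already enrolled at the higher dose.

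**Working it through.** **Calendar.** IFX-1 is given on Cycle 1 Days 1, 4, 8, 15, 22 and 36, then every two weeks (section 7.2.1.2). The next dose is Day 36 + 14 = Day 50. This reproduces the stated Cycle 1 length of 7 weeks: 7 × 7 = 49 days, so Cycle 2 Day 1 is Day 50.

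- Criterion 6: a delay of more than 14 days is first true on Day 50 + 15 = Day 65, and 65 − 36 = 29 days after the trigger. The ±3-day visit window puts Cycle 2 Day 1 at Day 47 to 53, giving Day 62 to 68, or 26 to 32 days after the trigger.
- Criterion 2, value first seen on Day 36: 36 + 7 = Day 43.
- Criterion 4, more than 7 days: 36 + 8 = Day 44.
- Criterion 8: an event after the Day 22 dose can cost at most 1 of 6 IFX-1 doses (17%) and none of the single Cycle 1 pembrolizumab dose, so it does not reach 25%.

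**Who is exposed at each decision.**

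- Regimen 1 to 2: patients 2 and 3. If the others enter the day after patient 1's Day 36 review, patient 1 is at Day 36 + 1 + 35 = Day 72 when they reach Day 36.
- Regimen 2 to 3: all three. The one-week stagger allows Days 36 + 7 = 43, 36 and 36 at the review.
- Regimen 3: there is no higher cohort. What is exposed is the RP2D decision, and the clearance of 1600 mg in at least three patients that permits intrapatient escalation (section 7.2.1.2).

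**A case under the protocol's own rules.** Biochemistry is drawn pre-dose on Day 36. Suppose it shows a Grade 2 immune-related ALT rise, and the Day 36 dose was given before the result was back. Grade 2 meets no DLT criterion at that point. Under section 7.2.2.2.1 and Appendix 8, Table 4, "both pembrolizumab and IFX-1 should be withheld" and steroids are started. The taper begins at Grade 1 or lower and lasts at least 4 weeks, and dosing may resume after the taper.

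| Back to Grade ≤1 | Earliest restart (+28 days) | Delay from Day 50 | Delay from Day 53 |
|---|---|---|---|
| Day 36 | Day 64 | 14 days (not a DLT) | 11 days (not a DLT) |
| Day 37 | Day 65 | 15 days (DLT) | 12 days (not a DLT) |
| Day 40 | Day 68 | 18 days (DLT) | 15 days (DLT) |

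**Illustration.** The documents give no DLT rates, so both inputs are assumed: p is the true DLT rate and f the share of DLTs known only after review. Let q = p(1 − f) be the rate visible at Day 36. I use the escalation rule of section 10.3.4.2 (0 of 3, or 1 of 6), reading the stopping rule as more than 1, as section 7.2.2.2.4 does. At the six-patient decision the first three are at Day 72 or later, so their late DLTs are taken as known and counted:

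P(escalate) = (1 − q)³ + 3q(1 − p)²(1 − q)³ = (1 − q)³[1 + 3q(1 − p)²]

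| p | f | q | (1 − q)³ | 3q(1 − p)² | P(escalate) |
|---|---|---|---|---|---|
| 30% | 0 | 0.300 | 0.3430 | 0.4410 | 49% |
| 30% | 10% | 0.270 | 0.3890 | 0.3969 | 54% |
| 30% | 25% | 0.225 | 0.4655 | 0.3308 | 62% |
| 30% | 50% | 0.150 | 0.6141 | 0.2205 | 75% |
| 40% | 0 | 0.400 | 0.2160 | 0.4320 | 31% |
| 40% | 10% | 0.360 | 0.2621 | 0.3888 | 36% |
| 40% | 25% | 0.300 | 0.3430 | 0.3240 | 45% |
| 40% | 50% | 0.200 | 0.5120 | 0.2160 | 62% |

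This describes regimen 2, where all three outcomes can be incomplete. In regimen 1 the effect is smaller because the first patient's outcome is complete.

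**The case against.** The best defense is committee discretion. Section 7.2.2.2.3 has dosing delays weighed for escalation purposes, section 5.3 has adverse events reviewed at every safety review in the manner of the DLT definition, and section 5.3.2 supplies all available safety data before each meeting. A patient on steroids with both drugs withheld would be visible, and a delay of more than two weeks may already be foreseeable. This stands as far as it goes: the committee may wait or call the DLT early. It is not required to do either, and the three-monthly meetings are not a hold before escalation. The Steering Committee Charter, which may say more, is not among the documents.

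It is also fair that the consequence is bounded. Pembrolizumab is 400 mg in every regimen. The regimen 3 IFX-1 dose is the Arm A dose, reviewed in three patients before Arm B opens. A late DLT (29 days after the trigger) would surface before the next cohort's own review, which needs at least 7 + 36 = 43 days. By then, however, that whole cohort could be enrolled.

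A reader might infer several stronger things that the documents do not support:

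- That every late Grade 2 immune-related event treated with steroids becomes a DLT. It does so only on the dates in the table, if dosing waits for a full 4-week taper, and if single-drug continuation with sponsor agreement (section 7.2.4.2) is not used. Table 4 also uses a steroid dose of 10 mg/day or less as a threshold for pembrolizumab, so full taper completion is one reading.
- That half of DLTs would be late, because Day 22 to Day 36 is 14 of the 28 days from the first pembrolizumab dose to Day 36. That is calendar time, not a share of DLTs; most non-hematologic events of Grade 3 or higher count at once under criterion 3.
- That late DLTs in the first three patients stay hidden at the six-patient decision. By then those patients are at Day 72 or later.

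**Conclusion.** The timing gap is real. The review trigger precedes completion of criterion 6 by about 29 days (26 to 32 with windows), and of the duration limbs of criteria 2 and 4 by 7 to 8 days for a value first seen on Day 36. The plan permits waiting but does not require it, and is silent on a DLT confirmed after review. The next cohort can therefore open on an incomplete count, mainly at regimen 1 to 2 and regimen 2 to 3.

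The dates follow from the protocol. The escalation percentages rest on assumed DLT rates and late shares, on a committee that acts at Day 36 without anticipating the delay, and on late DLTs being counted once known. They show direction and rough scale, not an estimate for this trial. It would go too far to say that the committee must escalate on a wrong count. Severity is low to moderate, and the improvement is cheap.

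**What to change.** Add two or three sentences across sections 7.2.2.2.3, 5.3.2 and 10.3.4.2:

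- A patient with an open related toxicity at Day 36 (study drug withheld, steroids started for an irAE, a Grade 4 hematologic value, or a Grade 3 or 4 laboratory value) is not counted as DLT-free until criterion 2, 4 or 6 is resolved. Escalation waits for that patient. If a Cycle 2 delay of more than two weeks is already unavoidable, the committee may count the DLT at once.
- A DLT confirmed after the review is added to its cohort's count. Enrollment and intrapatient escalation at the higher dose pause until the committee has re-reviewed.

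All other patients are cleared at Day 36 as now. The cost is a wait of up to about 29 days, only in cohorts with an open case.
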